## MEPS Outcomes and Statistical Data Analysis

### *Outcomes.*

Outcomes are indicators of achieving various milestones. Specific Aim 1 outcomes are measures of PrEP uptake: (a) primary care provider who can prescribe PrEP, (b) screening/evaluation for PrEP, (c) begin PrEP, (d) adhere to PrEP, (e) remain on PrEP for at least 3 months. Specific Aim 2 outcomes are whether study participants have sufficient preventive screening, (a) HIV screening every 3 months, (b) STI screening every 6 months, and (c) at least one HCV test. Specific Aim 3's outcome is that each participant be enrolled in appropriate SUDs treatment: (a) received any SUD treatment post-release; (b) attended some SUD treatment services appropriate to ASAM level; (c) met at least 70% of recommended treatment activities/frequencies for ASAM level of care. Outcomes of the secondary aims are (i) obtaining appropriate follow-up care for those who test positive for HIV, STI and HCV; (ii) lack of recidivism; and (iii) service utilization patterns. For all outcomes except the last, our primary hypothesis is that the control group will do worse, and our secondary hypothesis is that App+Incentives+PM arm will be more effective than the App+Incentives.

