The purpose of this study is to inform an intervention designed to reach a high-risk population at a critical point for increased risk of HIV infection – men who have sex with men (MSM) and transgender women (TG women) who have substance use disorders and are leaving jail. It will test a new intervention (called Mobile Enhanced Prevention Support or MEPS) that involves a GPS-based mobile app (called GeoPassport), incentives, and peer support for promoting the use of HIV prevention and related services by comparing it to the case management services that these individuals can routinely have access to following jail release. We hypothesize that the intervention will increase rates of service utilization and use of pre-exposure prophylaxis (PrEP) for HIV prevention over the standard-of-care case management.

Background

In the United States, men who have sex with men (MSM) and transgender women are disproportionately impacted by HIV. Those with criminal justice involvement have particularly high HIV burdens. HIV prevalence estimates in jail populations are four times those of the general US population, and MSM and transgender populations experience elevated rates of incarceration. A majority of people in jail have substance use disorders (SUDs). The period following community reentry from incarceration is critical for addressing potential risks of HIV/STI acquisition and negative sequelae of substance use. This study leverages recent Medi-Cal investments in treating populations with SUDs who are leaving incarceration by building on a new jail-based treatment program in the Los Angeles County jail.

Periods of incarceration disrupt stable social and sexual relationships.^{21, 22} Given the barriers and complex interactions that formerly incarcerated people must negotiate upon release, the experience of transitioning from the correctional setting to the community is marked by *shocks* to social and sexual networks. The network shocks experienced at the time of detention and release have important health implications for BMSM with CJI and even those connected more distally. For example among young men re-entering the community after detention, an estimated 50% report inconsistent social networks (interactions with different individuals pre- and post-incarceration).²³ These may contribute to diminished social support and increased risk taking behaviors.

Characteristics of the subject population

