Determine the effectiveness of the intervention compared with the standard-of-care in achieving the following:

1) PrEP-related outcomes following jail release (PrEP continuum of care):

- a) establish a primary care provider, who can prescribe PrEP,
- b) obtain screening for PrEP,
- c) begin PrEP,
- d) adhere to PrEP, and
- e) remain on PrEP for at least 3 months.

2) Infection and prevention screening tests in the community:

- a) HIV every 3 months,
- b) bacterial STIs every 6 months; and
- c) HCV at least once.

3) Obtaining and remaining engaged in treatment for substance use disorders (SUDs) in the community, according to each participant's recommended American Society of Addiction Medicine level of care.

Participant-related Study Methods

Overview

A total of 266 HIV-negative or HIV status unknown men who have sex with men (MSM) and transgender women (TGW) will be enrolled in this randomized controlled trial prior to being released from Men's Central Jail. Participants will be recruited from a unit of the jail that is designated as protective custody for self-identified gay and bisexual men and for transgender women. Participants will be randomized into either the standard-of-care condition or the intervention condition that involves an innovative new GPS-based mobile app and incentives for utilization of prevention-related services, in addition to the support of a Peer Mentor (app+incentives+PM). Each condition will include up to 150 participants. The standard-of-care condition will consist of the substance-abuse focused transitional case management and referral services provided by the LA Center for Alcohol and Drug Abuse's **Substance Treatment And Re-entry Transition program (Project START Program)**

1. Recruitment and screening

Study eligibility will be based on the following criteria:

- i. *Inclusion* 1) housed in K6G unit, 2) ages 18-44 years, 3) screens positive for SUDs via Project START, 4) reports condomless sexual intercourse with a male or male-to-female transgender woman in the six months prior to jail entry, 5) is likely to be remain custody for at least four more days, but less than 45 days based on scheduled court dates, current sentence, etc., 6) has not received an HIV diagnosis (based on self-report), and 7) plans to reside in Los Angeles County following jail release.

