Over the course of the study, intervention participants may receive up to \$500 total in gift card incentives for completing Passport activities. Most of these activities will take place over six months and are each valued at just \$5-15. These include medically related visits (HIV/STI/HCV screening, PrEP evaluation), substance abuse treatment appointments, in-person meetings with their study Peer Mentor or START program Case Manager, and non-medically related items on their Passports (e.g., support group meetings for gay and bisexual men or TG women or trainings at an employment service center). A full schedule of activities and the amount of accompanying incentives is provided below:

Passport Activity	Maximum	Amount
Link to a PCP who will prescribe PrEP	1	\$ 15
PrEP screening/evaluation	1	\$ 15
Begin PrEP	1	\$ 15
HCV test	1	\$ 15
STI tests	2	\$ 15
HIV tests	4	\$ 15
Substance abuse treatment services (including AA/NA meetings) or case managers	8-14	\$ 10
Meetings with PMs	14	\$ 5-15
Other	6-10	\$ 15

The Passport's incentive structure is designed to provide more compensation for those study components that are directly related to HIV/STD biomedical intervention or prevention, however, the largest portion is for SUD services that are likely to be recommended to occur much more frequently. Frequency for HIV (every 3 months)/STI (every 6 months)/HCV (at least once) screening is based on CDC recommendations for MSM at increased risk for HIV. For the SUD-related services, participants will only be compensated for the number of visits recommended per their American Society of Addiction Medicine (ASAM) level of care. In addition, the incentives are intended to encourage initial linkage visits to other needed services and then capped in order to avoid a situation in which participants repeatedly complete incentivized activities after they are no longer beneficial. Once participants take part in a particular service, resolve barriers to service access with a Peer Mentor, and identify providers they like, it is hoped that they will continue to engage with those services as, needed, regardless of the opportunity for an incentive.

c) Mobile Application

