If a serious, emergent risk of harm to a participant or other person is revealed during a participant interaction outside of jail, these steps may involve contacting an emergency response team. If a serious, emergent risk of harm to a participant or other person is revealed in the jail, the START team or study staff will inform the jail-based medical services personnel. Participants will be informed of these exceptions to confidentiality.

16. Potential risks to study participants

Interviewed participants will be subject to minimal risk through their participation, with the greatest risk resulting from potential disclosure of sensitive information that is shared with the study. As indicated above, extensive efforts are planned to minimize this risk. In addition, it is possible that the surveys or Peer Mentor interactions will cause some psychological discomfort, given the sensitive or private information. We will try to limit this by assuring privacy and confidentiality, using well-trained interviewers and Peer Mentors, clarifying the type of questions that will be asked prior to conducting the surveys, and using sufficiently private interview locations. Participants can opt not to answer specific questions.

a. Protection against risks

Participants will be made aware prior to the start of baseline survey that the assessments will include questions on sensitive issues such as sexual risk behaviors, substance use/abuse, and a mental health issues. Participants will be informed about these types of survey questions at the screening and again during the initial informed consent process. Intervention participants who are diagnosed with a sexually transmitted infection or other health condition during the encouraged screenings will receive support from their Peer Mentors in obtaining the follow-up care and treatment that they need.

Participants in the control arm can access the study team for referrals to free services or obtain these from LA CADA.

Interviewed participants will be informed about their rights as research subjects. They may withdraw at any time during the study without penalty or loss. Furthermore, interviewed participants will be told that unless required by law, only the study investigators, members of the project staff, representatives of UCLA Institutional Review Board, National Institutes of Health, and U.S. Office of Human Research Protections will have the authority to review study records. In such cases, they too will be required to

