### *Modeling Outcomes.*

Each outcome will be analyzed in longitudinal intention to treat using analyses of all available data from Baseline and 3-, 6-, and 12-month follow-up interviews, mobile app, and abstracted record data on utilization, as appropriate. For PrEP cascade outcomes from aim 1, the model is a logistic generalized linear mixed model (GLMM) with a random intercept for participants and a binary 0-1 outcome with 1 indicating success (screening for PrEP say) and 0 indicating a lack of success (not screening for PrEP). We generally do not expect participants to have any PrEP-related positive outcomes at baseline, and we anticipate using only follow-up data at 3, 6 and 12 months in the analysis of specific Aim 1 outcomes. The fixed effects will be a mean for every date (3, 6, 12 months) for each intervention group, for a total of 9 parameters. The first hypothesis is a test for each outcome of differences at 6 months; secondary tests are for differences at 3 months and at 12 months. If the three groups are different at a given time point, we will do pairwise comparisons among the treatments, particularly between the two intervention arms with and without PMs. Specific Aim 3 is similar, though there may be some participants with appropriate SUDs treatment prior to baseline, thus we will include the baseline observation as part of the outcome. At baseline, groups have not been affected by interventions, thus all groups will be the same, so there is one additional parameter for the baseline mean. Otherwise, the analysis is similar to Aim 1 outcome analyses.

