### *Modeling Issues and Sensitivity Analyses.*

Sensitivity analyses will include predictors that are predictive of missing visits or whose average levels differ across study arms. Predictors predictive of missingness are likely to occur; satisfactory randomization should prevent average predictor levels from differing across intervention groups. We will analyze missing visits as a binary outcome with logistic random intercept regression model as functions of key (baseline; time-fixed) predictors (for example: Baseline behavior (e.g. whether they had tested for HIV in the 3 months prior to baseline), age under 30 vs. 30+; type of SUD; ASAM Level I & II vs. III & IV; stimulant user vs. not; race/ethnicity; preferred substance, education level), prior to performing the final analysis. Variables that are significant predictors of missing visits will be included as predictors in sensitivity analyses of intervention effects. If substantial missingness occurs in key baseline predictors, we will use multiple imputation to fill in the missing predictors. The missing visit analysis omits the baseline time point, as the baseline observation is required. To evaluate randomization, we analyze the key baseline predictors as outcomes in a one-way ANOVA. If some of the predictors differ by intervention arm, they will be included in sensitivity analyses.

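### Follow-up care is compared between arms only among those who test positive, a group the intervention helps to form, so randomisation does not protect the comparison

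*SAP*

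**What the plan says.** SAP, Outcomes, lists three outcomes for the secondary aims. The first is "obtaining appropriate follow-up care for those who test positive for HIV, STI and HCV". The same section then states: "For all outcomes except the last, our primary hypothesis is that the control group will do worse". Only the third secondary outcome, on patterns of service use, is exempt, so follow-up care carries a directional between-arm hypothesis.

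SAP, Modeling Outcomes, opens with a general rule: "Each outcome will be analyzed in longitudinal intention to treat using analyses of all available data". The models that follow are written for Aims 1 to 3. None is given for the secondary outcomes, and no denominator is stated for this one.

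Several parts of the protocol bear on who becomes a known positive:

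- Aim 2 (Overview and aims) is "Infection and prevention screening tests in the community", covering HIV, bacterial STIs and HCV. Testing is therefore itself an efficacy target.
- Section 8b (Incentives) pays intervention participants $15 per test, for up to four HIV tests, two STI tests and one HCV test. Control participants get no such payment.
- Sections 4 and 9 describe surveys and record linkage. No study-run testing of both arms is described.
- Section 16a says, of people in the intervention arm, that those "who are diagnosed with a sexually transmitted infection or other health condition during the encouraged screenings will receive support from their Peer Mentors". The intervention may therefore also act on follow-up care directly.

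**The concern.** The test-positive group forms after randomisation, and the intervention is designed to enlarge it. If testing rises, the intervention arm's positives will include people who would have gone untested, and so undiagnosed, under control. Those extra people may be more or less inclined to obtain care than people who test without encouragement. A between-arm difference among positives then mixes any real effect on linkage to care with a difference in who was found.

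The report could show an apparent harm because the intervention found more infections, or an apparent benefit that is only selection. The planned sensitivity analyses do not address this: "Sensitivity analyses will include predictors that are predictive of missing visits or whose average levels differ across study arms". They cover missed visits and baseline imbalance, not selection into the positive group.

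**Working it through.** **No planned figure to reproduce.** The SAP gives no event count, effect size or power for this outcome. Its power section covers the 11 primary outcomes (5 + 3 + 3 under Aims 1 to 3), and follow-up care is not among them. Every input below is an assumption except where a source is named.

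**Step 1: selection with no effect on care.** Take infected participants, with infection equally common in both arms and in both halves. One half is engaged: tested .5 under control and .7 under intervention, follow-up .8 once positive. The other half is less engaged: tested .1 under control and *x* under intervention, follow-up .4 once positive. Follow-up does not depend on arm.

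Follow-up among positives = (.5 × engaged testing × .8 + .5 × other testing × .4) / (.5 × engaged testing + .5 × other testing).

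Control: (.20 + .02) / (.25 + .05) = .22/.30 = .733.

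| *x* | Intervention, among positives | Difference from control | In care per infected person (control .22) |
|---|---|---|---|
| .14 | .308/.42 = .733 | 0 | .308 |
| .2 | .32/.45 = .711 | -2 points | .32 |
| .3 | .34/.50 = .680 | -5 points | .34 |
| .5 | .38/.60 = .633 | -10 points | .38 |

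The first row is zero because testing rises by the same ratio in both halves (.7/.5 = .14/.1 = 1.4). In the other rows the intervention places more infected people in care yet looks worse among positives.

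**Step 2: the opposite direction.** Swap the follow-up rates (engaged .4, other half .8) and keep *x* = .5. Control: (.10 + .04)/.30 = .467. Intervention: (.14 + .20)/.60 = .567. The spurious difference is now +10 points, in favour of the intervention.

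**Step 3: a second model that allows a true benefit.** A share *tc* tests in either arm and has care probability *ca* once positive. A further share *ti* - *tc* tests only under the intervention and has care probability *cn*. The intervention adds a true benefit *b* to care for everyone. Then

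intervention minus control, among positives = *b* - (1 - *tc*/*ti*)(*ca* - *cn*).

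For testing, borrow .30 and .65 from the success probabilities in SAP, Power Calculations. The SAP does not say which outcome those belong to. The weight is 1 - .30/.65 = .538.

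- *ca* = .80, *cn* = .50, *b* = 0: -.538 × .30 = -.16.
- Same, *b* = +.10: -.06 (80.0% control, 73.8% intervention), so the sign is wrong.
- *ca* = *cn*, *b* = 0: no bias.
- *ca* = .40, *cn* = .80, *b* = 0: +.538 × .40 = +.22.

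**Step 4: an outcome counted over all randomised.** Use the *b* = +.10 case with 15% infected in each arm. Control: .15 × .30 × .80 = 3.6%. Intervention: .15 × (.30 × .90 + .35 × .60) = .15 × .48 = 7.2%. The sign is right. The figure depends on infection, however: if prevalence in the intervention arm were .036/.48 = 7.5%, the two arms would score the same despite better testing and better care.

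**Step 5: how many positives.** The protocol's 266 gives 133 per arm if allocation is equal. At 15% infected, expected positives are 133 × .15 × .30 = 6.0 against 133 × .15 × .65 = 13.0. With testing of .20 and .80 they are 4.0 against 16.0. Over 5% to 30% infected and these two testing pairs, control has about 1 to 12 positives and intervention about 4 to 32. Power for 50% against 70% in care is then .07 to .22. These counts ignore attrition, which the SAP puts at 25%.

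**The case against.** The strongest reply is that bias needs two things the documents do not establish: that the intervention changes the mix of people tested, and that the added people differ in their propensity for care. Control is not inert on testing either. Both arms receive customised referrals, and section 7 gives START case managers the Passports to encourage these services. Peer Mentor support could also produce a real gain in care larger than any selection effect; in the *x* = .5 row, a true benefit above 10 points would restore the sign. All of this stands as a limit on the size of the problem. It does not restore comparability of the two positive groups.

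A second reply is that the SAP promises intention to treat for each outcome and never states that the denominator is positives only. That is fair: the restriction is read from the outcome's own wording. But the SAP does not say how never-tested or never-positive participants would be scored, so it needs a clarifying change on either reading.

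A reader might infer that the SAP specifies a test that is biased against the intervention, with a spurious harm of about 10 points. The documents do not support that. The 10 points come from one assumed pattern, a fivefold rise in testing among the less engaged (.1 to .5) against a 1.4-fold rise among the engaged. Other patterns give zero or the opposite sign.

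**Conclusion.** The concern holds as a matter of design: a between-arm hypothesis is attached to a comparison within a group that forms after randomisation and that the intervention acts on. The comparison is not protected by randomisation. Its bias may be zero, negative or positive, and the documents cannot fix the size. The range of 0 to -10 points rests on assumed testing and follow-up rates, equal infection across arms and no true effect on care. Positives per arm are likely to be few, but any count rests on assumed prevalence and testing rates. The outcome is secondary and lies outside the 11 primary outcomes and the SAP's multiple-comparison rule, so no primary conclusion changes.

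**What to change.** In SAP, Outcomes, exempt follow-up care from the between-arm hypotheses, as is already done for the last secondary outcome. Report follow-up care among positives by arm as descriptive only, with no between-arm test, beside the numbers randomised, tested and tested positive in each arm.

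If a randomised comparison is wanted, add a supportive yes/no outcome over all randomised participants: tested positive and obtained follow-up care. State with it that it mixes testing, infection and linkage, that uninfected participants score 0, and that fewer infections would lower it. This matters because the protocol expects the intervention to raise PrEP use (opening statement of purpose) and to reduce new infections (section 18). It should therefore be read only with its components and not as a measure of linkage alone.

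The cost is SAP wording; the data are already planned. What is given up is a formal between-arm test of linkage among diagnosed people, which this design cannot support without further assumptions or testing of both arms independent of the intervention.

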### *Modeling Outcomes.*

Each outcome will be analyzed in longitudinal intention to treat using analyses of all available data from Baseline and 3-, 6-, and 12-month follow-up interviews, mobile app, and abstracted record data on utilization, as appropriate. For PrEP cascade outcomes from aim 1, the model is a logistic generalized linear mixed model (GLMM) with a random intercept for participants and a binary 0-1 outcome with 1 indicating success (screening for PrEP say) and 0 indicating a lack of success (not screening for PrEP). We generally do not expect participants to have any PrEP-related positive outcomes at baseline, and we anticipate using only follow-up data at 3, 6 and 12 months in the analysis of specific Aim 1 outcomes. The fixed effects will be a mean for every date (3, 6, 12 months) for each intervention group, for a total of 9 parameters. The first hypothesis is a test for each outcome of differences at 6 months; secondary tests are for differences at 3 months and at 12 months. If the three groups are different at a given time point, we will do pairwise comparisons among the treatments, particularly between the two intervention arms with and without PMs. Specific Aim 3 is similar, though there may be some participants with appropriate SUDs treatment prior to baseline, thus we will include the baseline observation as part of the outcome. At baseline, groups have not been affected by interventions, thus all groups will be the same, so there is one additional parameter for the baseline mean. Otherwise, the analysis is similar to Aim 1 outcome analyses.

For specific Aim 2, the question in analyzing outcomes is whether the intensity (mean count) of health care visits per unit time is the same among the three groups. Thus, the analysis is a Poisson GLMM with log link and an offset equal to the log of the time covered by each observation, which models rates of visits per unit time. The advantage of this over binary logit GLMM modeling of 1=yes=had at least one visit in the past three months versus 0=no=no visits past three months, is that the binary model penalizes or rewards participants inappropriately for going a few days longer or shorter than 90 days in between visits. The parameter structure and statistical hypothesis testing is the same as for aim 1, though we estimate rate ratios instead of odds ratios. We will estimate the difference between the desired rate of visits (one per 3 months or per 6 months or per year) and the actual observed rate in each intervention arm.

Initial data analysis includes checking for out-of-range data and data cleaning. We will plot average outcomes and error bars as plus or minus two standard errors of the mean as a function of visit, broken out by intervention arm. These are called empirical summary plots. Weiss (2005) describes our general approach to modeling longitudinal data as will be generated by this study. A GLMM random intercept model can be fit in the SAS software Proc Mixed (Cary, NC 2017); if there are problems fitting the data in Proc Mixed, we will move to Bayesian software such as JAGS in R.

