The data will be collected via Audio Computer Assisted Self-Interview (ACASI), where the survey is read to the participant via headphones and responses are recorded directly into the laptop. However if security issues occur that restrict the use of laptops, a pen-and-paper version of the survey will be used and for later entry into the database. The laptop will not contain a webcam and Wi-Fi will be disconnected/ disabled. The A-CASI method of collection and setting allows sufficient security and privacy to protect participants and the confidentiality of their information. The first follow-up interviews are intended for completion in the community. However, they will be conducted in jail if a participant is reincarcerated at that time. These surveys will last about 60 minutes. They will be conducted by a trained research assistant in a study office or a mutually agreeable and private field site.

5. Development of wellness plan (i.e., Passport)

Initial Passport Development will occur at the end of the interview process using pen-and-paper templates developed for this purpose. To aid this process, the Passport Developers will use a Summary Report generated within the survey software, based on participants' responses to the baseline assessment. This report will summarize potential sexual behavior and substance use risk factors, gaps in knowledge regarding HIV and STIs, history of PrEP use, prior testing for HIV, STIs and HCV, lack of access to primary or mental health care, lack of social support, religious conflict, and unmet needs in a range of areas (e.g., cash and nutrition benefits, housing) that the participant experienced prior to incarceration.

Using the Summary Report from the baseline assessment, the Passport Developer (either a trained full-time member of the study team or a trained substance abuse counselor from Project START) work with participants in the jail to determine which of the identified concerns he or she finds most problematic and is most motivated to address post release from jail. Goals related to PrEP uptake will vary based on participant's "stage of change" in this area and may range from accessing PrEP information from pre-identified, online sites to reestablishing an existing PrEP prescription on release. Activities related to SUDs will depend on the recommended American Society of Addiction Medicine (ASAM) level of care based on results of the screener for substance use disorders (SUDS) as defined by the DSM V.

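### The primary Aim 1 models leave out baseline PrEP and provider status on a premise that sits uneasily with the protocol; prespecifying it as a covariate costs little and protects the primary estimate against imbalance

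*SAP*

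**What the plan says.** **SAP, Modeling Outcomes.** The Aim 1 outcomes (provider who can prescribe PrEP, PrEP screening, start, adherence, three-month persistence) are fitted by a logistic mixed model with one mean per arm at 3, 6 and 12 months and no baseline term. The reason given is: "We generally do not expect participants to have any PrEP-related positive outcomes at baseline, and we anticipate using only follow-up data". For Aim 3 some participants may already be in suitable treatment, "thus we will include the baseline observation as part of the outcome", with one baseline mean common to all arms. For Aim 2 (testing rates): "The parameter structure and statistical hypothesis testing is the same as for aim 1".

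**SAP, Modeling Issues and Sensitivity Analyses.** Key baseline predictors are compared across arms. "If some of the predictors differ by intervention arm, they will be included in sensitivity analyses". The examples listed include baseline behaviour, illustrated by recent HIV testing. PrEP use and provider status are not named.

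**Protocol, section 1 (Recruitment and screening).** No criterion excludes current PrEP users or people who have a primary care provider.

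**Protocol, section 5 (wellness plan).** PrEP goals "may range from accessing PrEP information from pre-identified, online sites to reestablishing an existing PrEP prescription on release". The summary report drawn from the baseline assessment covers, among other things, "history of PrEP use, prior testing for HIV, STIs and HCV, lack of access to primary or mental health care".

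**Protocol, sections 2 and 6.** Everyone recruited in a given week or month receives the same assignment, and each person consents on a form that describes that arm.

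**The concern.** The SAP applies one line of reasoning to Aim 3 and does not carry it to Aim 1. If some people may already be in treatment, baseline belongs in the model. The protocol allows the same for PrEP prescriptions, and its eligibility criteria allow it for primary care providers. Information that probably predicts the Aim 1 outcomes is gathered before release and then kept out of the primary model.

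Two things are at stake. The first is power: a predictive covariate left out of a logistic model weakens the test. The second is the primary estimate itself. With whole weeks or months sharing an assignment, differences between periods become differences between arms. Because people know their arm when they consent, and only the intervention arm offers up to $500 for completed activities (Protocol, section 8b), those who agree may also differ systematically. If one arm enrols more people who already had a provider or used PrEP, the unadjusted comparison carries that difference.

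**Working it through.** **1. The plan's own power figures.** None of them uses baseline.
- Three-arm chi-square test, rates (0.025, 0.075, 0.15): the SAP gives 0.958 at 133 per arm and 86 (read as 0.86) at 100. An arcsine approximation gives 0.947 and 0.866; simulation of the Pearson test gives 0.942 and 0.847. These agree within 2 points.
- Pairwise, power 0.8: the SAP gives a detectable difference of 0.17 at 133 per arm and 0.20 at 100. Recomputed minimum power over the rates tried is 0.795 and 0.812. These agree.

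**2. Inputs for the check.**
- Rates 0.30 versus 0.50, the first two of one triple in the SAP's Power Calculations.
- n = 100 per arm, the SAP's figure after 25% attrition. The protocol's 266 gives 133 per arm, and 133 × 0.75 = 99.75.
- Not in the documents, so assumed: baseline prevalence q = 0 to 30%, and odds ratio (OR) between baseline status and 6-month success = 3 to 10.
- Simplification: the 6-month time point alone, without the random intercept and without clustering by period.

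**3. Unadjusted power.** Log OR = ln[(0.5/0.5)/(0.3/0.7)] = 0.847. Variance = [1/(0.3×0.7) + 1/(0.5×0.5)]/100 = 0.0876, SE 0.296. z = 2.862 and power = Φ(2.862 − 1.96) = 0.817.

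**4. Adjusted power.** Success rates by baseline status are chosen so that the overall rates stay at 0.30 and 0.50. Information is summed over the two baseline strata, each contributing n·w / [1/(p0(1−p0)) + 1/(p1(1−p1))], where w is the stratum share.

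Example, q = 10%, OR = 10:
- Control rates are 0.248 (baseline negative) and 0.767 (positive). Intervention rates are 0.456 and 0.894.
- Information = 9.58 + 0.62 = 10.20, so variance = 0.0980 and SE = 0.313.
- Conditional log OR = 0.934, z = 2.982, power = Φ(1.022) = 0.847.

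| Assumed q | Power, OR 3 | Power, OR 10 |
|---|---|---|
| 0% | 0.817 | 0.817 |
| 5% | 0.821 | 0.832 |
| 10% | 0.825 | 0.847 |
| 20% | 0.832 | 0.872 |
| 30% | 0.836 | 0.888 |

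In the example the variance rises (0.0876 to 0.0980) while the log OR rises from 0.847 to 0.934. Power improves because the conditional effect is larger, so the adjusted and unadjusted odds ratios are different quantities.

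For rarer outcomes, 0.025 versus 0.10, power goes from 0.528 to at most 0.567. For 0.30 versus 0.65 unadjusted power is already 0.999.

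**5. Imbalance.** The SD of the chance difference in baseline prevalence is √[2q(1−q)/n × (1 + (m−1)·ICC)], with m people per randomization period.
- Individual randomization (m = 1): 3.1 points at q = 5%, 6.5 points at q = 30%.
- Assuming m = 20 and ICC = 0.05, the factor is 1 + 19×0.05 = 1.95. At q = 30% the SD becomes 9.0 points.

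A 10-point imbalance shifts the control 6-month rate by about 2.4 to 5.2 points. Scaling to one SD: 3.1 × 0.26 = 0.8 points (q = 5%, OR 3, individual randomization), up to 9.0 × 0.49 = 4.4 points (q = 30%, OR 10, period assignment). Selection through arm-specific consent would come on top, and the documents allow no figure for it.

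**The case against.** The SAP's wording is hedged: it speaks of what is generally expected and of what it anticipates doing. A reader might infer that the SAP assumes nobody is positive and that the protocol flatly contradicts it. The documents do not support that. Section 5 of the protocol describes the span of possible goals and gives no prevalence, and its summary report flags lack of care access, which does not show that many have a provider.

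A reader might also infer that a prior PrEP user counts as a success in either arm. That is not so. The aim is stated as "PrEP-related outcomes following jail release (PrEP continuum of care", and a prior user is described as "reestablishing an existing PrEP prescription on release", which still requires action after release. For adherence and three-month persistence, pre-jail use is only a proxy.

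A large loss of power is likewise unsupported. With half the sample positive at baseline and success of 0.8 versus 0.3, the linear-model shortcut gives r² = 0.25×0.25/(0.55×0.45) = 0.253 and 266/(1 − 0.253) = 356, an apparent 34% gain in sample size. The planned model is logistic; with the same prevalence and association and rates of 0.30 versus 0.50, the gain is 24%. Those inputs are themselves generous, and if the SAP's premise holds the gain is nil.

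Chance imbalance is ordinary sampling error and does not bias a randomized comparison, and a shift of 0.8 to 4.4 points is modest beside a 20-point detectable difference. The sensitivity analyses offer some protection. All of this stands and limits the size of the point. It does not answer why the primary model omits baseline when Aim 3 includes it, or why the fallback waits for an observed imbalance and does not name the most relevant variables.

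**Conclusion.** The point holds in moderate form. The Aim 1 premise is in tension with the protocol, most clearly for having a provider and for existing PrEP prescriptions, and least for adherence and persistence. Aim 2 appears to inherit the same structure, but that is an inference: the follow-up-only sentence names Aim 1 alone, and the section opens by promising all available data, including baseline, as appropriate.

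The power gain from adjustment runs from zero to about 7 points for 0.30 versus 0.50 at 100 per arm. It is at most about 3 points at prevalence up to 10%, and more than that only with 20–30% prevalence and a strong association. These figures rest on assumed prevalence and association and on a single-time-point approximation.

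The firmer reason to act is that assignment by period with arm-specific consent makes baseline imbalance more likely, and the planned response leaves the primary estimate unadjusted. A covariate corrects only for what is measured, so it does not fully resolve selection at consent.

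**What to change.** In the SAP's Modeling Outcomes section:

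1. Prespecify fixed baseline covariates in the primary models: pre-jail primary care provider or care access for 1(a), pre-jail PrEP use for 1(b)–(e), and pre-jail HIV, STI and HCV testing for 2(a)–(c). Where an outcome has a true baseline version, the Aim 3 structure with a common baseline mean is an alternative.
2. Remove or soften the statement that PrEP-related positives are not expected, and give the expected baseline prevalence.
3. State outright whether Aim 2 uses baseline.
4. Name PrEP and provider status among the key baseline predictors.
5. State that the adjusted odds ratio is conditional, or report a standardised risk difference beside it.

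The cost is SAP wording and one or two parameters per model. The protocol lists these topics for the baseline assessment, but the survey itself is not among the documents. The team should confirm the items exist, in particular whether a provider can prescribe PrEP; if that is not asked, care access is the available proxy. If very few participants turn out to be positive for an outcome, the covariate adds little, and the SAP should say in advance what happens if it cannot be estimated.
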